## **Primary Outcome Analysis**

## **Secondary Outcomes Analyses**

### **Safety**

***Safety will be summarized using*** the number and proportion of patients reporting any given event and will be tabulated by treatment received according to the worst severity experienced. Separate tables will be constructed for (a) all reported events, (b) procedure related events, (c) serious events. Event rates will be compared between treatment arms by Fisher's exact test.

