
Study Design
	
This is a randomized controlled trial designed to test efficacy of 4Q-TAP against TEA (routine of care) on quality of recovery 48 hours after CRS-HIPEC surgery. All patients will be enrolled at MD Anderson Cancer Center.

Number of Patients
	
160 patients randomized to the 2 study arms (80 patients per arm)

Sites
	
MD Anderson Cancer Center

Duration of Study	It is expected that this will take up to 36 months.
Duration of Patient Participation	Patients who consented to participate in the study will remain in the study until last planned outcome is collected on postoperative day 30. Patient will have the opportunity to withdraw from the study at any time.
Primary Endpoint Definition	Quality of recovery (QoR) 48 hours after CRS-HIPEC surgery.
Secondary Endpoints	
 
• Postoperative pain 48 hours
 
• The total opioid consumption within 48 hours after surgery
 
• Length of stay
 
• Incidence of adverse events
 
• Incidence of opioid-related adverse events
 
• Postoperative complications and morbidity
 
• QoR on postoperative day 3, 7 10 and 30.
 

Primary Safety Endpoint	All reported adverse events.
Follow-Up Schedule	The study will be considered complete after all randomized patients have had 30 days of follow-up data collection.
Inclusion Criteria	
 
1. Written informed consent;
 
2. 18 years old or older;
 
3. American Society of Anesthesiologists physical status (ASA) 1-3;
 
4. Scheduled surgery: open elective CRS-HIPEC;
 
5. Able to complete the QoR 15 questionnaire;
 
6. Patients scheduled to receive intraoperative chemotherapy;
 

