## 2. STUDY OBJECTIVES

a. To evaluate impact of 4 quadrants TAP blocks (4Q-TAP) versus Thoracic Epidural Analgesia (routine care) on the quality of recovery and other clinically relevant outcomes after CRS-HIPEC surgery.

b. To study the incidence of adverse events associated with (4Q-TAP) blocks versus Thoracic Epidural Analgesia (routine care) after CRS-HIPEC surgery.

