## 3. STUDY AIMS

a. **Primary Aim:** To compare the efficacy of 4 quadrants TAP blocks (4Q-TAP) versus Thoracic Epidural Analgesia (routine care) on the quality of recovery 48 hours after CRS-HIPEC surgery.

**Hypothesis:** The quality of recovery with 4 quadrants TAP blocks (4Q-TAP) 48 hs after CRS-HIPEC surgery is not inferior to Thoracic Epidural Analgesia (routine care).

b. **Secondary Aim 1:** To compare the efficacy of 4 quadrants TAP blocks (4Q-TAP) versus Thoracic Epidural Analgesia (routine of care) on

postoperative pain 48 hours after CRS-HIPEC surgery.

**Hypothesis:** Postoperative pain 48 hours after CRS-HIPEC surgery is not inferior with 4 quadrants TAP blocks (4Q-TAP) than Thoracic Epidural Analgesia (routine care).

c. **Secondary Aim 2:** To compare the total opioid consumption between patients with 4 quadrants TAP blocks (4Q-TAP) versus Thoracic Epidural Analgesia (routine care) intraoperatively and up to 48 hours after CRS-HIPEC surgery.

**Hypothesis:** Perioperative opioid consumption after CRS-HIPEC surgery is not higher in patients with 4 quadrants TAP blocks (4Q-TAP) than epidural analgesia (routine care).

d. **Secondary Aim 3:** To compare the length of stay (LOS) between patients with 4 quadrants TAP blocks (4Q-TAP) versus Thoracic Epidural Analgesia (routine care) after CRS-HIPEC surgery.

**Hypothesis:** The LOS after CRS-HIPEC surgery is shorter in patients with 4 quadrants TAP blocks (4Q-TAP) than Thoracic Epidural Analgesia (routine care).

e. **Secondary Aim 4.** To compare the incidence of adverse events (i.e. postoperative hypotension, failed block) related to 4 quadrants TAP blocks (4Q-TAP) versus Thoracic Epidural Analgesia (routine care) 48 hours after CRS-HIPEC surgery.

**Hypothesis:** The incidence of adverse events (i.e. postoperative hypotension, failed block) related to 4 quadrants TAP blocks (4Q-TAP) is lower than Thoracic Epidural Analgesia (routine care) 48 hours after CRS-HIPEC surgery.

f. **Secondary Aim 5.** To compare the incidence of opioid-related adverse (i.e. respiratory depression, pruritus, sedation, delirium) events related to 4 quadrants TAP blocks (4Q-TAP) versus Thoracic Epidural Analgesia (routine care) 48 hours after CRS-HIPEC surgery.

**Hypothesis:** The incidence of opioid-related adverse events is lower in patients receiving 4 quadrants TAP blocks (4Q-TAP) versus Thoracic Epidural Analgesia (routine care) 48 hours after CRS-HIPEC surgery.

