## **B. Interventions**

Patients will be randomized 1:1 on the morning of surgery to one of the following 2 interventions:

**TEAgroup:** Patients in this group will be treated as standard of care. An epidural catheter will be placed before induction of anesthesia by an anesthesiologist. The catheter will be placed between the thoracic vertebral spaces 8 and 12 according to routine care. A bolus or infusion of local anesthetic solution with or without the addition opioids will be given before surgical incision according to anesthesia provider's clinical judgment. If deemed appropriate, a pre-incision epidural bolus of hydromorphone (300-800 micrograms) may be administered according to the anesthesia provider's clinical judgment.

**4Q-TAP block group:** Patients in this group will have an ultrasound guided 4Q-TAP block. A maximum of 80 cc of a solution consisting of 30 mg of bupivacaine HCl in 10 cc of PFNS and 65 mg of liposomal bupivacaine in 10 cc of PFNS will be injected before surgical incision in each of the four quadrants.

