### **Statistical Considerations**

The primary objective of evaluating the impact of 4 quadrants TAP blocks (4Q-TAP) versus Thoracic Epidural Analgesia (TEA - routine care) on the quality of recovery (QoR) will be conducted using total scores on each patient acquired from the QoR-15. The QoR-15, as previously mentioned, is a validated instrument with well-studied psychometric properties used to measure postoperative quality of recovery. The QoR-15 consists of 15 items. All 15 items follow a Likert scale ranging from 0 to 10 (where “0” refers to none of the time [poor] and “10” refers to all of the time [excellent]). A patient’s total score is the sum score across all 15

items (note: the last 5 items are reverse scored). The lowest score a patient can receive is “0” and the highest score is “150”; where higher total scores indicate better quality of recovery. To evaluate the trial changes in QoR-15 total scores will be computed for each treatment arm. The changes will be compared between patients receiving 4Q-TAP Block and patients receiving TEA. Figure 1 illustrates the trial’s development over time. Once a patient is randomized and the preoperative QoR-15 is administered, which takes approximately 2.4 minutes to complete, patients will be provided postoperative QoR-15 approximately 26 hours after surgery (Figure 1: [A]; Stark et al). Within patient changes from baseline will be computed for each treatment arm. These changes will be compared between treatment arms (Figure 1: [B]).

Figure 1: Trial Schema

This randomized trial will be used to determine if 4Q-TAP Block is non-inferior to TEA based on postoperative changes in QoR-15 using a non-inferiority margin of 10 units. According to Stark et al., the reported mean change in QoR-15 before and after surgery is -22 (95%CI: -26 to -18) based on 127 adults. This information allowed us to assume of a common standard deviation of 23 units for the change in QoR-15’s total score pertaining to each treatment arm, which was ultimately used to derive the study’s sample size.

[figure not shown]
The following hypothesis test will be used to evaluate the trial:

$$H_0: \mu_{4Q-TAP\ Block} - \mu_{TEA} \geq 10.0$$

$$H_a: \mu_{4Q-TAP\ Block} - \mu_{TEA} = 0 \text{ (rejecting } H_0 \text{ implies non-inferiority)}$$

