We will use a one-sided t-test test with a significance level of 0.05 and power of 80%. A non-inferiority margin of 10 was considered by assuming an average change in QoR-15 of -25 units in the TEA arm and that the average change in QoR-15 for the 4Q-TAP Block treatment arm would be no greater than -35.

Figure 2: Non-inferiority assessment

These specifications require an approximate sample size of 140 patients as indicated in Table 1. Moreover, an interim analysis will be conducted at after 70 patients are randomized using stopping boundaries provided by the method of Pock and Simon. At the interim, the trial will stop early if  $p < 0.006$  for efficacy and  $p > 0.367$  for futility (East v6).

Table 1: Estimated sample size given projected study parameters

Expected QoR-15 Avg. Change * for Epidural group	Non-inferiority Margin	Power	Alpha (1-sided)	Approx Sample Size
-25	10	80%	5%	140

\*Avg. Change before and after surgery; Assumed SD = 23; A non-inferiority margin of 10 implies the Avg. Change for TAP will be -35 [ie.  $-25 - (-35) = 10$ ]

\*Sample size for the difference of two means using a two sample test (East v6).

The data will be evaluated per protocol for patients contributing analyzable data.

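### Fisher's exact test for event rates is valid but conservative; Boschloo's test, ordered by the two-sided Fisher p-value, is never less powerful and costs one sentence

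*Combined protocol and SAP*

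**What the plan says.** The Safety paragraph under Secondary Outcomes Analyses describes tables of all, procedure-related and serious events by treatment received, then states: "Event rates will be compared between treatment arms by Fisher's exact test". It gives no significance level, sidedness, effect estimate or interval.

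Event incidence matters to the trial. Objective (b) in section 2 reads "To study the incidence of adverse events associated with (4Q-TAP) blocks versus Thoracic Epidural Analgesia (routine care) after CRS-HIPEC surgery". In section 3, the Aim 4 hypothesis is that the incidence of events such as hypotension and failed block "is lower than Thoracic Epidural Analgesia (routine care) 48 hours after CRS-HIPEC surgery". The Aim 5 hypothesis begins "The incidence of opioid-related adverse events is lower in patients receiving 4 quadrants TAP blocks (4Q-TAP".

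The synopsis plans "160 patients randomized to the 2 study arms (80 patients per arm", and the Interventions section says "Patients will be randomized 1:1 on the morning of surgery". The only test level in the plan belongs to the primary comparison: "We will use a one-sided t-test test with a significance level of 0.05 and power of 80" per cent.

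An earlier paragraph, also headed Safety and within Statistical Considerations, includes everyone who receives any part of either treatment. It assigns dichotomous outcomes to univariable and multivariable logistic regression.

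**The concern.** Fisher's test conditions on the total number of events. The design does not fix that total before the data are seen. Because the conditional distribution is discrete, the true error rate usually falls below the nominal level, and the unused part is lost power. An exact unconditional test can recover some of it and still guarantee the nominal level whatever the common event rate.

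At stake is the chance of detecting a real difference in event rates, in a trial whose size was set for QoR-15. Whether any reported error rate is too high is not in question.

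**Working it through.** **Inputs.** Arm sizes are 80/80 (synopsis) and 70/70 (the computed total of 140 in Statistical Considerations). Nearby unequal splits were added because safety is tabulated by treatment received. Two-sided 5% is an assumption. For event rates, the Background puts epidural failure, an Aim 4 event, at about 10% and up to 30%; all other rates are assumptions.

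**The plan's own figure.** There is none for the event comparisons. The total of 140 belongs to the primary test, planned "using a non-inferiority margin of 10 units" with SD 23, one-sided 0.05 and 80% power. A fixed design needs 2 × (1.645 + 0.842)² × 23² / 10² = 65.4, so 66 per arm and 132 in total. Adding one look at half the information, with O'Brien-Fleming-type alpha and beta spending and non-binding futility, gives 139.5, so 140. It also gives interim limits of 0.0056 and 0.367, against the stated 0.006 and 0.367. The figure of 70 per arm is therefore sound as an input.

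**Method.** List every table (x events of n₁, y of n₂) and compute its two-sided Fisher p-value, p_F(x, y).

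- True size at common rate π: the sum of b(x; n₁, π) × b(y; n₂, π) over rejected tables, where b is the binomial probability. The maximum is taken over a grid of 1,999 values of π.
- Fisher rejects when p_F ≤ 0.05.
- Boschloo rejects when p_F ≤ c, where c is the largest cutoff whose maximum size is at most 0.05. Since Fisher's own maximum is below 0.05, c is at least 0.05, so Boschloo's region contains Fisher's.
- Power is the same sum with a different rate in each arm.

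**Maximum true size, nominal two-sided 5%**

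| Arms | Fisher | Boschloo | Cutoff c | Extra tables rejected |
|---|---|---|---|---|
| 70/70 | 3.42% | 4.93% | 0.0626 | 80 |
| 80/80 | 3.46% | 4.89% | 0.0697 | 120 |
| 69/71 | 4.27% | 4.98% | 0.0587 | 44 |
| 79/81 | 4.20% | 4.99% | 0.0567 | 46 |
| 78/82 | 4.20% | 4.97% | 0.0561 | 42 |
| 77/83 | 4.21% | 4.99% | 0.0563 | 48 |

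Exactly equal arms make the conditional distribution symmetric, so the two tails tie and fewer distinct p-values are available. That is why Fisher loses most there. At 80/80 its size is 0.2% at a common rate of 2%, 1.6% at 5%, 2.8% at 10% and 3.3% at 30%.

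**Power, Fisher to Boschloo (TEA rate first)**

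| Rates | 70/70 | 80/80 | TEA 79, 4Q-TAP 81 |
|---|---|---|---|
| 10% v 2% | 36.2 to 47.5% | 44.3 to 54.5% | 54.4 to 58.3% |
| 20% v 5% | 72.2 to 76.0% | 79.3 to 83.0% | 83.5 to 83.9% |
| 30% v 10% | 81.3 to 83.1% | 86.7 to 89.7% | 88.9 to 89.7% |
| 30% v 15% | 49.4 to 52.8% | 56.3 to 62.1% | 60.2 to 61.8% |
| 40% v 20% | 68.3 to 71.9% | 74.5 to 79.4% | 77.2 to 78.7% |

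Ten pairs of rates were checked: these five plus 10% v 5%, 15% v 5%, 20% v 8%, 30% v 12% and 50% v 30%. With equal arms the gain runs from 1.8 to 11.2 points. With unequal arms and TEA the smaller arm, it runs from 0.4 to 9.7 points (9.7 is 10% v 2% at 77/83). With TEA the larger arm it can vanish: for 10% v 2% with 82 on TEA and 78 on 4Q-TAP, both tests have 47.4% power.

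**One table.** 25/70 v 14/70 gives Fisher p = 0.059. This is below the 70/70 cutoff of 0.0626, so Boschloo rejects where Fisher does not (software p = 0.041).

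**The ordering matters.** Some software, including the scipy routine, builds the two-sided Boschloo p-value from one-sided tests. For 10/79 v 3/81, Fisher gives p = 0.046 and that routine gives 0.052, so a Fisher rejection is lost. This cannot happen with the two-sided Fisher ordering.

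**Other levels.** At nominal one-sided 5%, Fisher's maximum is 3.78% (70/70) and 3.64% (80/80). At one-sided 2.5% it is 1.71% and 1.73%.

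**The case against.** The strongest reply is that keeping Fisher's test is a legitimate choice. It is valid, familiar, and controls error conditionally as well as overall. In a randomised comparison the event total is fixed under the sharp null hypothesis, so conditioning can be defended. The plan states no multiplicity control for its many event comparisons, and mild conservatism there does little harm. All of this stands. It limits the point to efficiency and does not remove it, because the alternative gives the same unconditional guarantee and loses no rejection.

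A reader might infer four stronger things that the documents do not support:

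- *The test will run at 3.4% instead of 5%.* The plan states no level, 3.4% is a maximum, and it needs exactly equal arms. Tabulation by treatment received does not secure that.
- *Fisher's test decides Aims 4 and 5.* The plan attaches it to the event tables and gives dichotomous outcomes to logistic regression too, without saying which governs.
- *Any two-sided Boschloo test dominates Fisher's.* The 10/79 v 3/81 table shows otherwise.
- *The case for 4Q-TAP rests on these comparisons alone.* The Background and Rationale also cite patients who cannot receive TEA and lower use of resources, and Aim 3 expects a shorter stay.

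**Conclusion.** The point holds as an optional efficiency gain in secondary and safety comparisons. Fisher's test is not an error, and no conclusion drawn from it would be invalid. With the ordering specified, Boschloo's test is never less powerful at the same level. The benefit is worthwhile if the safety arms are equal and often small if they are not. It tends to be largest for rare events, except where the larger arm is TEA.

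The containment of Fisher's rejection region follows from the definition of the test. The size figures rest on the assumed two-sided 5% level, and the power figures also on the assumed event rates.

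**What to change.** In the Safety paragraph under Secondary Outcomes Analyses, replace the Fisher sentence, for event yes/no comparisons, with wording such as: *Event rates will be compared between arms by Boschloo's exact unconditional test at two-sided 5%, using the two-sided Fisher p-value as the test statistic and the actual safety arm sizes; the risk difference will be reported with an exact unconditional 95% confidence interval.*

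Add that this test, rather than the logistic regression in Statistical Considerations, decides Secondary Aims 4 and 5. Tables by severity grade stay descriptive, since the test applies to two-by-two tables only.

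The cost is a short text amendment, made before event data are seen by arm, and a check that the software uses the stated ordering. If it does not, the enumeration above takes seconds to program. No patients or data are added. Multiplicity across the event comparisons is a separate matter that this change does not address.

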## **Data Management – Data Collection and Processing**

Study data will be collected and managed using REDCap (Research Electronic Data Capture) electronic data capture tools hosted at MD Anderson. REDCap ([www.project-redcap.org](http://www.project-redcap.org)) is a secure, web-based application with controlled access designed to support data capture for research studies, providing: 1) an intuitive interface for validated data entry; 2) audit trails for tracking data manipulation and export procedures; 3) automated export procedures for seamless downloads to common statistical packages; and 4)

procedures for importing data from external sources.

REDCap (<https://redcap.mdanderson.org>) is hosted on a secure server by MD Anderson Cancer Center's Department of Research Information Systems & Technology Services. REDCap has undergone a Governance Risk & Compliance Assessment (May 2014) by MD Anderson's Information Security Office and found to be compliant with HIPAA, Texas Administrative Codes 202-203, University of Texas Policy 165, federal regulations outlined in 21 CFR Part 11, and UTMDACC Institutional Policy #ADM0335. Those having access to the data file include the study PI and research team personnel. Users are authenticated against MDACC's Active Directory system. The application is accessed through Secure Socket Layer (SSL). All protected health information (PHI) will be removed from the data when it is exported from REDCap for analysis. All dates for a given patient will be shifted by a randomly generated number between 0 and 160, thus preserving the distance between dates. Dates for each patient will be shifted by a different randomly generated number.

Following publication study data will be archived in REDCap. Since study data may be useful for future research studies performed under separate IRB approved protocols, study data will be archived indefinitely in REDCap. Since REDCap is a secure electronic database with controlled access, and because patient identifiers may be needed to link study data to data from other sources under future IRB approved protocols, patient identifying information will be retained in the archived database.

Investigators are responsible for the accurate completion and timely submission of the data collected during the study. Quality assurance procedures will be established to ensure that complete, accurate and timely data are submitted, that protocol requirements are followed and that complications, adverse events and adverse device effects are correctly reported and investigated, as appropriate. Investigators are to maintain all source documents as required by the protocol, including laboratory results, supporting medical records, and signed Informed Consent forms. The source documents will be used during the regular monitoring visits to verify information from the database against data contained on the completed CRFs.

The Principal Investigator must maintain detailed records on all patients who sign the Informed Consent and begin the pre-procedure evaluation. Data for enrolled patients will be entered directly into the electronic Case Report Forms (eCRFs) in REDCap. For source documents, corrections should be made in a manner that does not obscure or eliminate the original error, by striking through the original data with one line, and initialing and dating the change, along with the reason for the change.

Study exit eCRFs are completed for all enrolled patients, regardless of whether they did or did not complete the Study (e.g., patient discontinuation, study termination).

## Monitoring Procedures

Monitoring visits to the clinical sites will be made periodically during the study, to ensure that all aspects of the current, approved protocol/amendment(s) are followed. Original source documents will be reviewed for verification of data in the database. In the event that the original medical records cannot be obtained for a patient that is seen by a non-study physician at a non-study institution, photocopies of the original source documents must be made available for review. It is important that the Investigator and relevant study personnel are available during the monitoring visits and that sufficient time is devoted to the process. Phone contacts and site visits will be conducted to ensure that the protocol is being followed and that any protocol deviations are properly documented. Clinical monitoring will include a verification that Informed Consent was properly obtained for all enrolled study participants, a review of clinical records for accuracy and completeness, resolution of missing or inconsistent results and a review of source documents. The clinical monitor will verify that the CRFs are in agreement with the source documentation and other records. The investigator will make available to the clinical monitor for review all Informed Consent documents, Internet access to completed CRFs, source documentation, original laboratory data and other relevant records for all enrolled patients at the site. It is important that the investigator and other relevant site personnel are available for consultation with the clinical monitors during the monitoring visits and that sufficient time is devoted at the site to the monitoring process. Additionally, telephone and/or e-mail contact will be conducted on a regular basis with the investigator and the site staff to ensure that the protocol is being followed and to address any issues that may occur during the course of the study.

If a deficiency is noted during an on-site visit (or at any other time during the course of the study), the clinical monitor is required to discuss the situation with the investigator to secure compliance. Monitoring visit will begin after enrollment of first 3 patients.

